7.4.3 Permitted Concomitant Therapy

The following medications will be permitted during the study:

- Antihistamines
- Antiemetics
- Antidiarrheals
- Aspirin
- Nonsteroidal anti-inflammatory drugs (NSAIDs)

7.4.4 Supportive Care Guidelines for Atezolizumab Treatment

Subjects should receive appropriate supportive care measures as deemed necessary by the treating investigator related to atezolizumab treatment. Guidance regarding the identification, evaluation, and supportive care measure for the management of these events with potential immunologic etiology, including infusion-related reactions, are outlined in [Appendix F](#). Where appropriate, these guidelines include the use of corticosteroids, additional anti-inflammatory agents, or other concomitant medications if symptoms do not improve with administration of corticosteroids. For each disorder, attempts should be made to rule out other causes such as metastatic disease or bacterial or viral infection, which might require additional supportive care. These treatment guidelines are intended to be applied when the Investigator determines the events to be related to atezolizumab. Note, if after the evaluation the event is determined to be not related, the Investigator is instructed to follow the reporting guidance but does not need to

follow the treatment guidance (summarized in [Appendix F](#) along with dose modification guidelines).

7.4.4.1 Infusion-related Reactions

Symptoms that occur during or within 24 hours after an infusion of atezolizumab may be part of an acute infusion reaction. The non-serious symptoms should be recorded as separate AEs on the AE eCRF. Serious symptoms should be reported as one SAE with the most medically significant sign or symptom as the primary event term. Additional signs and symptoms should be reported in the 'Additional Case Details' section of the AE eCRF page.

Infusion-related reactions will be managed according to severity according to the following procedures:

- In the event that a patient experiences a mild infusion-related event (National Cancer Institute Common Toxicity Criteria for Adverse Events [NCI CTCAE] Grade 1), the infusion rate should be reduced to half the rate being given at the time of event onset. Once the event has resolved, the Investigator should wait 30 minutes while delivering the infusion at the reduced rate. If tolerated, the infusion rate may then be increased to the original rate.
- In the event that a patient experiences a moderate infusion-related event (NCI CTCAE Grade 2) or flushing, fever, or throat pain, the patient should have his or her infusion immediately interrupted and should receive aggressive symptomatic treatment. The infusion should be restarted only after the symptoms have adequately resolved to baseline grade. The infusion rate at restart should be half the infusion rate that was in progress at the time of the onset of the infusion-related event.
- For severe or life-threatening infusion-related events (NCI CTCAE Grade 3 or 4), the infusion should be stopped immediately, and aggressive resuscitation and supportive measures should be initiated. Patients experiencing severe or life-threatening infusion-related events will not receive further infusion and will be further managed as clinically indicated until the event resolves.

Further details regarding the management of Infusion-related reactions are provided in [Appendix F](#).

7.5 Diet/Activity/Other Considerations

7.5.1 Diet

Subjects should maintain a normal diet unless modifications are required to manage an AE such as diarrhea, nausea, or vomiting.

7.5.2 Contraception

Animal reproduction studies have not been conducted with CMB305 to evaluate the effect of the components on reproduction or fetal development. Atezolizumab may have adverse effects on a fetus *in utero* and it is not known if atezolizumab therapy has any adverse effects on the composition of sperm. Furthermore, human IgGs are known to cross the placental barrier and the PD-1/PD-L1 pathway has been linked with pregnancy maintenance.³¹

Currently, there is no human data demonstrating the effects of this line of CPI therapy in pregnancy, lactation, or reproductive potential. Therefore, non-pregnant, non-breast-feeding women may only be enrolled into the trial if they are willing to use 2 methods of birth control or are considered highly unlikely to conceive. Highly unlikely to conceive is defined as:

1. Surgically sterilized,
2. Postmenopausal (a woman who is ≥ 45 years of age and has not had menses for greater than 1 year will be considered postmenopausal), or
3. Not heterosexually active for the duration of the study.

The 2 birth control methods can be either 2 barrier methods, or a barrier method plus a hormonal method to prevent pregnancy. Subjects should start using birth control from Study Visit 1 throughout the study period up to 90 days after the last dose of study therapy.

The following are considered adequate barrier methods of contraception: diaphragm, condom (by the partner), copper intrauterine device, sponge, or spermicide as per local regulations or guidelines. Appropriate hormonal contraceptives will include any registered and marketed contraceptive agent that contains an estrogen and/or a progestational agent (including oral, SC, intrauterine, or IM agents).

Subjects should be informed that taking the study medication may involve unknown risks to the fetus (unborn baby) if pregnancy were to occur during the study. In order to participate in the study, they must adhere to the contraception requirement (described above) for the duration of the study and during the follow-up period. If there is any question that a patient will not reliably comply with the requirements for contraception, that patient should not be entered into the study.

It is unknown whether atezolizumab or any components of CMB305 are excreted in human milk. Since many drugs are excreted in human milk, and because of the potential for serious adverse reactions in the nursing infant, subjects who are breast-feeding are not eligible for enrollment.

8.0 STUDY PROCEDURES

This study will be conducted in compliance with the protocol approved by the Institutional Review Board (IRB), and according to GCP standards. No deviation from the protocol will be implemented without the prior review and approval of the IRB, except where it may be necessary to eliminate an immediate hazard to a research patient. In such case, the deviation will be reported to the IRB as soon as possible (also see [Section 16.2](#)).

8.1 Visit Windows

Visits from Day 0 to 105 will have a window of ± 3 days from the specified study day. Follow-up phase visits (after Day 105) will have a window of ± 4 days. Refer to the Schedule of Events ([Table 1](#) and [Table 2](#)) for the timing of visits and the specific procedures that will be performed at each visit.

8.2 Study Visits

8.2.1 Screening Visit(s): Weeks -4 to 0 (Days -30 to -1)

Patients will undergo screening and enrollment procedures up to 30 days prior to Study Day 0. Assessments may occur at multiple visits. Screening procedures/assessments include the following:

1. Consent for assessment of tumor biopsy surgical specimen

No trial-specific staging or biopsy procedures will be undertaken prior to completion of the consenting process. However, if a patient has had tests performed prior to providing informed consent as part of standard of care (considered standard for the patient and routine medical practice, based upon their presentation at the time), and ALL of the following conditions are met, then these data may be allowed as part of the study data:

- The tests fulfill all requirements of the study, i.e., are complete and follow the procedures outlined in the study;
- The tests have been completed within the specified number of days to perform pre-treatment assessments; and
- It is medically unwise to repeat a test/procedure or it poses undue additional risk to the patient.

NY-ESO-1 expression will be determined for pre-study tumor samples by IHC. Tumor tissue specimens from any prior surgical resection or biopsy may be examined for NY-ESO-1 expression, and the analysis will be performed by a central lab. A separate screening consent form will be available and may be used to screen patient tumor samples for NY-ESO-1 expression prior to signing the primary consent form for participation on this clinical study. However, pre- and on-study biopsies may also be required for immune testing if lesions are accessible.

NY-ESO-1 testing results of tumor tissue obtained in conjunction with a different IMDZ study may also be used to qualify for this trial if the testing was performed by an IMDZ-approved central lab. For this study, there is no time limit on when the test was performed and the use of its results to qualify for this study. Confirmation of NY-ESO-1 expression should be made before beginning other screening procedures. Tumor histology including an evaluation of immune cell invasion and composition will also be examined.

2. Informed consent/Human Insurance Portability and Accountability Act (HIPAA) authorization
Prior to study enrollment, each patient will receive complete information, both verbally and in writing, about the nature of the study, the anticipated risks, discomfort associated with the study, and about the right to interrupt participation in the study at any time. Prior to participation in the study, each patient (or representative) will have signed the written, IRB-approved Informed Consent Form (ICF) and HIPAA form. This should be done within 30 days prior to their anticipated dosing start date (Day 0). An agreement to continue in the study and obtain tumor biopsy if the patient meets the criteria for progressive disease but wishes to remain on study should also be obtained.
3. Review of inclusion/exclusion criteria and determination of patient eligibility ([Section 6.0](#)).
4. Demographics
5. Medical history – includes a review of systems, general medical and surgical history, concomitant illnesses, current medications, and tumor-specific therapy history. Oncologic baseline disease characteristics/history will be recorded (diagnosis, disease stage, ECOG status [[Appendix A](#)], and RECIST lesions [[Appendix C](#)]). (Any changes to Medical History from initial collection of data to Day -1 should be updated to the records.)
6. Full Physical examination, including height, weight, vital signs (including temperature, respiratory rate, HR, and resting BP), and 12-lead ECG.
7. Assessment of diagnosis and stage of disease (tumor staging), including Computed Tomography (CT) of chest, abdomen, pelvis. Other assessments such as magnetic resonance imaging (MRI), bone scan or positron emission tomography (PET)/CT should be performed only if indicated for the cancer indication.
8. Blood sample collection. Up to 78 mL of blood will be collected for the following evaluations:
 - HIV/HepB/HepC testing (5 mL) – As part of study eligibility, patients must have a negative HIV test at screening. LV305 is an engineered LV that contains genes originally derived from HIV and it is not known if treatment with LV305 will result in seroconversion of patients to positive upon HIV screening. Secondary confirmatory assays such as Western Blot can be used to demonstrate that the normal complement of HIV proteins is not present (unless the patient has developed a true HIV infection). Patients in the combined treatment arm will be provided with a card from the study Sponsor describing the possibility of a screening test becoming positive and the importance of confirmatory testing. In the event a study patient should have a positive

screening HIV test, the site should inform and consult IMDZ for recommendations on the most appropriate confirmatory test to use.

- Cellular immunity (approximately 55 mL) – collected in 8 CPT™ Heparin tubes for T-Cell response assays and performed at sites where staff are trained in peripheral blood mononuclear cell (PBMC) isolation.
- Safety laboratory evaluations (10 mL) – includes hematology and clinical chemistry.
- LV305 persistence testing (8 mL) – Only for those subjects randomized to the combination treatment arm.

9. Urinalysis

10. Urine pregnancy test for FCBPs

11. Thyroid function tests (triiodothyronine [T₃], thyroxine [T₄], and thyroid stimulating hormone [TSH])

12. Tumor biopsy (for patients who provide consent for the biopsy procedure). The pre-treatment biopsy must be completed ≤ 6 months prior to screening. If unavailable, a new biopsy may be performed.

13. Randomization and enrollment into the study

Once patients have been properly consented, and all inclusion/exclusion and screening criteria have been documented as being met, patients will be enrolled into the study. Randomization must occur no more than 4 days before Day 0.

8.2.2 Treatment Phase (Weeks 0-12 Treatment Visits, Study Days 0 to 84)

The following procedures will be performed at all study visits for subjects in both treatment arms:

1. AEs and SAEs (including MEOIs)
2. Concomitant Medications
3. Vital Signs (temperature, HR, resting BP) obtained pre-dose and 30 minutes, post-dose. For the first atezolizumab infusion, the patient's vital signs (HR, respiratory rate, BP, and temperature) should be measured within 15 minute of the infusion, during the 60-minute infusion (every 15 [± 5] minutes), and 30 minutes after the infusion. For subsequent infusions, vital signs do not need to be obtained during the infusion if the prior infusion was tolerated without symptoms.
4. Physical examination: simple targeted physical examination
5. ECOG status
6. Urine pregnancy test for FCBP on treatment days. Note: pregnancy test must be performed within 72 hours before study drug administration and negative before study drug administration.
7. Blood samples (10 mL) for safety laboratory evaluations within 4 days before treatment initiation and up to 48 hours before each subsequent dose.

The following procedures will occur at select study visits according to the study visit schedule provided in [Table 1](#) and [Table 2](#):

- Blood samples will be collected at selected sites on Study Days 0, 42, and 70 for immunological assessments including cellular immunity (55 mL).
- A blood sample will be collected at Study Day 84 for thyroid function tests.
- Tumor Staging: includes CT scans to evaluate progression per RECIST/irRC will be performed every 6 weeks. MRI, bone scans or PET/CT will only be performed if clinically necessary.
- Tumor biopsy on Days 0 and 42
- Patients in the combination treatment arm will receive study drug LV305 at Study Day 0, Week 2, 6, and 10; G305 will be administered at Weeks 4, 8, and 12.
- Atezolizumab will be administered every 3 weeks (Weeks 0, 3, 6, 9, and 12).

8.2.3 Post-CMB305 Long-term Treatment Study Visits

Following the Treatment Phase, patients in the combined treatment arm will enter the Booster Phase (post Day 84 to 1 year post Day 0); patients who complete the Booster Phase will then enter the Maintenance phase (1 year to 2 years post Day 0). Patients in the control arm will enter the Maintenance Phase (post Day 84 to 2 years post Day 0).

8.2.3.1 Booster Phase (Combined Treatment Arm Only: post Day 84 to 1 year post Day 0)

The following procedures will be performed in the combined treatment arm during these visits:

1. AEs and SAEs (including MEOIs)
2. Concomitant Medications
3. Vital Signs
4. Physical examination: simple targeted examination
5. ECOG status
6. A G305 booster will be given in the combined treatment arm 6 weeks following the Day 84 dose and every 6 weeks thereafter for 1 year (from Day 0) or until disease progression.
7. Atezolizumab administration will be administered on Day 105 and every 3 weeks thereafter for 1 year (from Day 0) or until toxicity develops or progression. After Day 105, one of three atezolizumab doses may be delayed by 1 week (28 days instead of 21 days for one cycle) to allow for vacations.
8. Urine pregnancy test must be performed for FCBP within 72 hours before study drug administration and negative before study drug administration, if patients are still receiving booster doses of G305 and/or atezolizumab.

Blood samples for cellular immunity (55 mL) and a tumor biopsy will occur on Day 98 (\pm 2 weeks) and the following procedures will occur on Day 105:

- 12-lead ECG
- Blood for safety laboratory evaluations (10 mL)
- Urine pregnancy test for FCBPs
- Administration of atezolizumab

All subjects will return to the clinic every 3 weeks for 1 year (from Day 0) or until disease progression (whichever is later) for the following assessments:

1. AEs and SAEs (including MEOIs; only those possibly related to study drug will be reported)
2. Concomitant Medications (only those related will be reported)
3. Vital Signs
4. Physical Examination (symptom-specific)
5. ECOG status
6. Blood for safety laboratory evaluations (10 mL)
7. Thyroid function tests should be monitored at least every 3 months
8. Tumor staging by CT every 6 weeks for the first year, then every 12 weeks

The following procedures will occur at select study visits according to the study visit schedule provided in [Table 1](#):

- A tumor biopsy should be performed at 6 months or longer (for patients with treatment response) and at the time of progression
- A blood sample will be collected at Day 168 for HIV testing (5 mL).
- Blood samples will be collected at Day 168

8.2.3.2 Maintenance Phase (Combined Treatment Arm: From 1 Year to 2 Years Post Day 0; Control Arm: Post Day 84 to 2 Years Post Day 0)

The following procedures will be performed these visits:

1. AEs and SAEs (including MEOIs)
2. Concomitant Medications
3. Vital Signs
4. Physical examination: simple targeted examination
5. ECOG status
6. For patients in the control arm, atezolizumab administration will be administered on Day 105 and every 3 weeks thereafter for 1 year (from Day 0) or until toxicity develops or progression. After Day 105, one of three atezolizumab doses may be delayed by 1 week (28

days instead of 21 days for one cycle) to allow for vacations. For patients in the combined treatment arm, atezolizumab administration will continue to be administered every 3 weeks for 1 year (from 1 year to 2 year post Day 0) or until toxicity develops or progression.

7. Urine pregnancy test must be performed for FCBP within 72 hours before study drug administration and negative before study drug administration, if patients are still receiving booster doses of G305 and/or atezolizumab.

For patients in the control arm, blood samples for cellular immunity (55 mL) and a tumor biopsy will occur on Day 98 (\pm 2 weeks) and the following procedures will occur on Day 105:

- 12-lead ECG
- Blood for safety laboratory evaluations (10 mL)
- Urine pregnancy test for FCBPs
- Administration of atezolizumab

All subjects will return to the clinic every 3 weeks for the following assessments:

1. AEs and SAEs (including MEOIs; only those possibly related to study drug will be reported)
2. Concomitant Medications (only those related will be reported)
3. Vital Signs
4. Physical Examination (symptom-specific)
5. ECOG status
6. Blood for safety laboratory evaluations (10 mL)
7. Thyroid function tests should be monitored at least every 3 months
8. Tumor staging by CT every 6 weeks for the first year, then every 12 weeks

The following procedures will occur at select study visits according to the study visit schedule provided in [Table 1](#):

- A tumor biopsy should be performed at 6 months or longer (for patients in the control arm with treatment response) and at the time of progression
- For patients in the control arm, a blood sample will be collected at Day 168 for HIV testing (5 mL).
- Blood samples will be collected at Day 168 (controlled arm), then again at 12 and 24 months (post Day 0) for LV305 persistence testing (8 mL).

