
Safety Monitoring
	
The safety profiles for CMB305 and atezolizumab are described in their respective Investigator’s Brochures (IBs). Safety will be monitored by evaluating solicited and spontaneously reported adverse events (AEs), including reactogenicity, symptoms, physical examination findings, vital signs, laboratory findings, and discontinuations for AEs. AE severity assessments will be performed using National Cancer Institute (NCI) Common Terminology Criteria for Adverse Events (CTCAE) v4.03. All adverse events, regardless of relationship to study drug, should be reported until 30 days after the last dose of study drug or until initiation of another anti-cancer therapy, whichever occurs first.
 
AEs (both non-serious and serious) associated with exposure to the study drugs may represent an immunologic etiology. These AEs may occur shortly after the first dose or several months after the last dose of treatment. The study drugs must be withheld for drug-related toxicities as outlined in Appendix F, as well as severe or life-threatening AEs.
 
Data Monitoring Committee
 
A DMC will operate in accordance with a signed charter and will consist of 2 experienced oncologists familiar with clinical use of the study drugs and an ad hoc biostatistician who is knowledgeable about statistical methods for clinical trials and sequential analysis of trial data. The DMC will review all cumulative safety information from the Safety Run-in prior to recommendations for further patient enrollment. Thereafter, the DMC will provide independent review of all safety data every 3 months to minimize risks to study patients. All DLTs and SAEs considered at least possibly related to study regimen will be reviewed by the DMC and the Sponsor as they are reported and on an ongoing basis. These reviews may lead to modification or stopping of the treatment program if related, treatment-emergent adverse events indicate a safety profile that is inconsistent or significantly worse than reported with the use of either CMB305 or atezolizumab

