Procedures	Timeline – Days	-30 to -1	0	14	21	28	42	56	63	70	84	98	105			
Informed consent/HIPAA ^c	X															
Inclusion/exclusion criteria	X															
Demographics/Medical History	X															
Tumor-specific therapy history	X															
NY-ESO-1 expression on pre-study tumor sample ^d	X															
Enrollment and randomization		X														
Report AEs and SAEs		X	X	X	X	X	X	X	X	X	X	X	X	X	X	
Record any previous concomitant meds	X	X	X	X	X	X	X	X	X	X	X	X	X	X	X	
Vital signs ^e	X	X	X	X	X	X	X	X	X	X	X	X	X	X	X	
Physical exam ^f	X	X	X	X	X	X	X	X	X	X	X	X	X	X	X	
ECG (12-Lead)	X											X				
Tumor staging, by CT scan ^g	X					X				X			X	X		
ECOG	X	X	X	X	X	X	X	X	X	X	X	X	X	X	X	
HIV, HepB, and HepC (5 mL) ^h	X												X ^h	X ^h		
Blood for cellular immunity (55 mL) ⁱ	X	X				X			X		X ⁱ					
Blood for safety labs (10 mL) ^j	X	X	X	X	X	X	X	X	X	X		X	X	X		
Thyroid function tests ^k	X									X			X ^k	X ^k		
Urinalysis	X															
Urine sample for pregnancy test ^l	X	X	X	X	X	X	X	X	X	X		X	X	X		
Study drug: LV305		X	X			X			X							
Study drug: G305					X		X			X			X ^m			
Study drug: atezolizumab		X		X		X		X		X		X ⁿ	X ⁿ	X ⁿ		
Blood for LV305 persistence (8 mL) ^o	X												X ^o	X ^o		
Tumor biopsy ^p	X					X					X ^p			X ^b		
Survival Status															X ^q	
Blood volume per visit (mL)	78	65	10	10	10	65	10	10	65	10	55	10				
Total blood volume	78	14	15	16	17	23	24	25	32	333	38	398				
		3	3	3	3	8	8	8	3		8					

Immune Design
CMB305 (LV305 and G305) and Atezolizumab
Protocol IMDZ-C232; Version 03, Release Date 08Mar2017

Abbreviations: AE = adverse event, CT = computed tomography; ECG = electrocardiogram; ECOG = Eastern Cooperative Oncology Group; HepB = hepatitis B; HepC = hepatitis C; HIPAA = Human insurance Portability and Accountability Act; HIV = Human immunodeficiency Virus; meds = medications; mos = months; PBMC = peripheral blood mononuclear cells; SAE = serious adverse event.

- a. A window of ± 3 days is permitted for Visits 3 through 12. Follow-up phase visits (Visits 13+) will be permitted a window of ± 4 days, Tumor assessments will be permitted a window of ± 1 week.

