9.0 ASSESSMENTS OF EFFICACY AND SAFETY

9.1 Timing of Assessments

The timing of study assessments is summarized in the Schedules of Events for each treatment arm ([Table 1](#) and [Table 2](#)) and detailed in [Section 8.2](#) (Study Conduct). After five cycles of atezolizumab administration, one of three cycles may be delayed by 1 week (28 days instead of 21 days for one cycle) to allow for vacations.

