9.4 Safety Assessments

Safety will be evaluated for all treated patients using NCI CTCAE v4.03.²⁹ Safety assessments will be based on medical review of both solicited and spontaneously reported AEs, SAEs, and MEOIs including symptoms, physical examination findings, vital signs, laboratory findings, ECGs, and discontinuations for AEs. After initiation of study drug, all AEs, regardless of relationship to study drug, will be reported until 30 days after the last dose of study drug or until initiation of another anti-cancer therapy, whichever occurs first.

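### The 3-weekly visit lists in Protocol 8.2.3.1 and 8.2.3.2 limit AE, SAE, MEOI and medication reporting to related items while patients are still being dosed, against the protocol's own all-causality rule

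*Protocol*

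**What the plan says.** Protocol 8.2.3.1 (Booster Phase) and 8.2.3.2 (Maintenance Phase) each contain two assessment lists for the same phase.

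- The first list opens with "AEs and SAEs (including MEOIs" and then concomitant medications, both without limit.
- The second list, for the 3-weekly clinic visits of all subjects, has "AEs and SAEs (including MEOIs; only those possibly related to study drug will be reported" and "Concomitant Medications (only those related will be reported".

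Elsewhere the protocol is broader. The synopsis (Safety Monitoring) states: "All adverse events, regardless of relationship to study drug, should be reported until 30 days after the last dose of study drug". Section 9.4 agrees: "all AEs, regardless of relationship to study drug, will be reported until 30 days after the last dose of study drug". Both add an earlier stop if another anti-cancer therapy begins. Sections 9.4.4 and 9.4.5 ask for AEs at every study visit. Section 9.4.6 takes all SAEs from Day 0 to 30 days after study drug stops, or to new anti-cancer therapy if that is earlier. Section 9.4.8 takes MEOIs to 90 days after treatment stops, or 30 days after new anti-cancer therapy, whichever is earlier. The row "Report AEs and SAEs" in Table 1, its counterpart in Table 2, and the medication rows carry no relatedness footnote.

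SAP 7.8.1 defines treatment-emergent AEs by onset and tabulates all of them separately from the related ones. SAP 7.8.10 summarises all concomitant medications.

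**The concern.** A site working through the 3-weekly list would leave an unrelated AE or medication off the case report form, while a site working from 9.4 would enter the AE. Safety is a secondary endpoint, and the SAP's distinction between all TEAEs and related TEAEs needs the unrelated ones to have been recorded. Under the restricted lists, what reaches the tables after the first three months or so depends on investigators' attribution in an open-label trial. It also depends on which passage each site follows. The DMC's periodic reviews of all AEs (Protocol 5.8) would draw on the same data. For medications, the lists do not even say what an item must be related to.

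**Working it through.** The plan gives no figure to reproduce, so the check compares the texts and then measures how much of the schedule the wording covers.

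**1. Are patients on drug when the restricted lists apply?** Yes. Both sections schedule atezolizumab every 3 weeks in the same period, and 8.2.3.1 adds G305 boosters in the first year. For a treated patient the 30-day post-dose period has therefore not begun.

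**2. Event reporting, side by side**

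| Place | Relatedness limit during treatment plus 30 days? |
|---|---|
| 8.2.3.1 and 8.2.3.2, second lists | Yes |
| 8.2.3.1 and 8.2.3.2, first lists | No |
| Synopsis; 9.4 | No, expressly all causes |
| 9.4.4; 9.4.5 | No, AEs at each visit |
| 9.4.6 (SAEs) | No; causal filter only afterwards |
| 9.4.8 (MEOIs) | No, within its own window |

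After the 30-day window, limiting SAEs to related ones agrees with 9.4.4 and 9.4.6, so the conflict stops there.

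**3. Medications.** The conflict is narrower. It is with the unrestricted first lists and with Protocol 5.1, which has non-protocol systemic anti-cancer therapy given before radiographic progression recorded as concomitant medication. Tables 1 and 2 simply carry no limit. The AE passages in 9.4 set no scope for medications.

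**4. Does any text decide which list prevails?** Section 8.1 sends sites to Tables 1 and 2 "for the timing of visits and the specific procedures that will be performed at each visit". Section 9.1 begins "The timing of study assessments is summarized in the Schedules of Events for each treatment arm" and then points to 8.2 for the detail. SAP Section 8 gives the SAP precedence over the protocol's statistical text, but an analysis rule cannot restore data that were never entered.

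**5. Reach of the wording, for a patient treated for the full 2 years (taken as 730 days)**

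- From Day 84: (730 − 84)/730 = 646/730 = 88%.
- From Day 105, the last individually scheduled visit: (730 − 105)/730 = 625/730 = 86%.
- Three-weekly visits after Day 105: 126 + 21k ≤ 730 gives k = 0 to 28, so 29 visits, the last on Day 714.
- Earlier post-screening visits: 11 in the combination arm (Visits 2–12, Table 1) and 8 in the control arm (Visits 2–9, Table 2).
- Shares of visits: 29/(11 + 29) = 29/40 and 29/(8 + 29) = 29/37.

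**6. How many patients get that far?** SAP Section 4 assumes exponential PFS with medians of 3 and 5.2 months. Taking progression-free status as a proxy for being on treatment (an assumption, since 6.3 allows treatment past progression), the share remaining is 2^(−t/median), with t in months of 30.4375 days for the day-based times.

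| Time | Median 3 months | Median 5.2 months |
|---|---|---|
| Day 84 | 53% | 69% |
| Day 105 | 45% | 63% |
| 24 months | 0.4% | 4.1% |

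On these assumptions roughly half to two thirds of patients enter the affected period, but at most about 3 of 80 (80 × 0.041 = 3.3) would reach its end.

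**The case against.** The strongest reply is that the protocol already points towards all-causality reporting. The synopsis and 9.4 say so outright, 9.4.5 puts AEs on the case report form at each visit, and the unrestricted first list covers the same phase. Section 9.1 defers to 8.2 on timing, which is not the same as scope. This has weight: a careful site would probably follow 9.4. But no sentence says that 9.4 overrides the visit lists, and the visit lists are what a coordinator uses.

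Two benign readings fail. The limit cannot be meant only for patients off drug, because the lists cover all subjects at the 3-weekly visits where drug is given. Nor can it mean expedited reporting only: 9.4.5 uses the same verb for entries on the AE page, and the limit is also applied to medications, for which no expedited route is described.

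Other parts of the reply stand. SAEs and MEOIs have a separate 24-hour route with no relatedness limit in their windows, so the practical exposure is mainly unrelated non-serious AEs and medications. Tables 1 and 2 are silent on relatedness and also mark the AE row under Survival Follow-up, where 9.4.4 does restrict, so they are weak evidence by themselves. Sections 9.4.1 to 9.4.3 and 9.4.7 do not conflict.

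A reader might also infer that 9.4.4 must be widened to collect non-serious related AEs after 30 days, because SAP 7.8.1 counts late related AEs as treatment-emergent. It need not be. The SAP classifies such events if they are recorded, and narrower collection does not contradict that. Patients who have progressed and stopped drug are then followed only by quarterly contact with their physician or a database search (8.2.4).

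**Conclusion.** The contradiction is real for patients on treatment and within 30 days of the last dose, and within the 9.4.8 window for MEOIs. It should be fixed because it determines which AEs and medications reach the safety tables and the DMC. If the restricted lists are followed, the all-causality TEAE and medication tables would be incomplete from about Day 84 to 105 onward and filtered by open-label attribution.

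Three stronger readings are not supported.

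- The 86% to 88% of days, and the 29 of 40 and 29 of 37 visits, are not shares of safety data lost. They describe a patient treated for the full 2 years. The number of events lost cannot be derived and is zero if sites follow 9.4.
- The wording is the same for both arms, so the rule itself does not favour either. Whether attribution would differ by arm cannot be told from the documents.
- The primary endpoints (OS and PFS) and the DLT window (first 42 days) are untouched.

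**What to change.** In the 3-weekly lists of 8.2.3.1 and 8.2.3.2, delete both parentheticals. For the scope and windows of AEs, SAEs and MEOIs, refer to 9.4, 9.4.4 to 9.4.6 and 9.4.8. Record all concomitant medications at these visits, as the first lists do and as Tables 1 and 2 allow. Do not add a new end window for medications, and leave the collection of subsequent anti-cancer therapy in follow-up (Protocol 8.2.4, SAP 7.8.11) as it is, because time to next treatment depends on it.

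If data have already been collected under the restricted wording, say so beside the TEAE and medication tables.

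A separate point to settle in the same amendment: the synopsis, 9.4 and 9.4.6 end AE or SAE reporting early when a new anti-cancer therapy starts, but 9.4.4 and SAP 7.8.1 do not mention this. These passages should be reconciled to one rule.

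The cost is four deletions, a few cross-references, one aligned cut-off, and some extra form entry at visits that already take place.
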